Two EHR vendors (eClinicalWorks and AthenaHealth) serve 11 of 13 Utah FQHCs and are widely used in FQHCs nationwide. The University of Utah, where pain teleconsult services will be hosted, uses Epic, the lead EHR vendor in academic medical centers. As described in our preliminary work (*see section C.3*), the University's Department of Biomedical Informatics team has enabled tobacco quitline reminders and e-referrals as a part of the PCORI-funded QuitSMART Utah trial. We plan to leverage a similar solution in this project. DIRECT connections between eClinicalWorks, AthenaHealth and Epic have been setup in other states. The University of Utah uses DIRECT for e-referrals to other health care networks in Utah and neighboring states as well as to the Utah quitline. We will follow a similar approach to implement pain teleconsult e-referrals from FQHCs in this project.

**D.9 Study Outcome Measures and Data Collection:** We will finalize the primary and secondary study outcomes in collaboration with the HEAL PRISM program in the Planning year. We will work with the PRISM program to insure that any common data elements of the HEAL initiative are incorporated.

We have developed our expected outcomes and schedule for administration (Table 5) balancing the collection of a broad array of patient-centered measures with a pragmatic study that endeavors to minimize participant burden. We will work with PRISM to harmonize outcomes with other program projects as appropriate. We plan to use pain interference as the primary study outcome because it reflects the degree to which pain interferes with daily activities, which is a hallmark of HICP. Patients with chronic pain often prioritize the functional impact of pain, and this outcome cannot be inferred from pain intensity as correlations are modest. Pain interference is a recommended outcome for chronic pain trials by IMMPACT and specifically for back pain clinical trials by the NIH Task Force on Research Standards for Chronic Low Back Pain. The NIH-funded Patient Reported Outcomes Measurement Information System (PROMIS) developed measures to quantify pain interference with physical, emotional and social activities using robust psychometric methods. We will use a PROMIS pain interference 8-item short form with established reliability, validity and responsiveness equivalent to legacy pain

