After completing the initial brief pain teleconsult session all participants will be scheduled for a follow-up phone session after about 1 week. For those randomized to only the Brief Pain Teleconsult the second session will include only the activities outlined in Table 2. After completion of the second session individuals in the Brief Teleconsult only treatment arm will be instructed to continue with their physical activity program and consult primary care provider as needed. For participants randomized to Phone-Based PT, the second session will include the activities listed in Table 2 for the second teleconsult session and then will transition to the 10-week phone-based PT protocol (Table 3). All participants will be followed-up at 12 weeks post-enrollment, coinciding with the conclusion of the first treatment phase (Fig.4).

Randomization will be administered in RedCap randomization module using schedules developed in the Planning year. We will stratify randomization based on pre-specified sub-grouping variables opioid use, gender, presence of HICP; and we may consider other stratification variables such as site during the Planning year.

**D.16.1 – Data Collection:** Consistent with a pragmatic study we have kept the number of assessments low which will facilitate phone-based data collection. We anticipate this will be our primary means of data collection. Research assistants will enter participant responses into a project platform in RedCap. We will finalize data collection and management plans in collaboration with the HEAL PRISM Data Coordinating Center. We will assess treatment fidelity to the brief pain teleconsult and phone-based PT using self-report checklists completed by the pain teleconsultants at each session recording core components of each intervention arm as detailed in our finalized study protocol.

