***D.18.1 General Considerations.*** Our data analyses will address the four aims defined in Section D.12. Aims 1 and 2 constitute the co-primary aims for comparison of effectiveness of the experimental interventions in the study. Aim 3 constitutes exploratory comparisons of effectiveness of the interventions in pre-specified subgroups, and Aim 4 addresses descriptive summaries of implementation outcomes. We anticipate using the PROMIS pain interference (PROMIS-PI) as the primary outcome for comparisons of effectiveness (*see Section D.9*), with key secondary outcomes including additional PROMIS domains and opioid use (Table 5). Aims 1-3 addressing the effectiveness of study interventions will follow the intention-to-treat principle, with all patients analyzed according to their randomized treatment assignment irrespective of adherence; exploratory analyses will summarize the association of outcomes with implementation and adherence measures. Aim 4 will use primarily descriptive statistics to examine implementation outcomes.

While one of our treatment strategies constitutes an adaptive intervention whose 2nd treatment phase is modified based on phase 1 response, our design has a single randomization and intention-to-treat comparisons of the two randomized groups compare the average effectiveness of initial assignment to the two different regimens (brief pain teleconsult only vs. brief pain teleconsult + phone-based PT). Aim 1 analyses compare outcomes at 12 weeks to compare the effectiveness of Phase I treatment – A) brief pain teleconsult alone, or B) brief pain teleconsult with phone-based PT as first line therapy. Aim 2 analyses compare long-term outcomes (52 weeks as primary comparison) between the same 2 regimens to compare effectiveness of a strategy in which phone-based PT is provided as first-line therapy vs. an adaptive strategy in which phone-based PT is added only for patients who fail to respond to initial treatment of brief pain teleconsult only. Because Aims 1 and 2 will be considered co-primary and address fundamentally distinct issues concerning the intervention regimens, we do not plan to use multiple comparison adjustment of our type I error rate ( $p < 0.05$ ) across the two aims.

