***Co-Primary Analyses of Aims 1 and 2:*** Reflecting the longitudinal design, the co-primary analyses of Aims 1 and 2 will use longitudinal mixed effect analyses of the primary effectiveness outcome scores (PROMIS-PI) at baseline, and across the 12-, 26-, and 52-week follow-ups, while assuming equal baseline mean PI scores across randomized groups to optimize statistical power. Linear contrasts will compare outcomes between randomized groups at 12 weeks to address Aim 1, and at 26 and 52 weeks (primary comparison) for Aim 2. Analogous linear mixed models or generalized estimating equations under general linear models will compare other secondary outcomes between the randomized groups.

Under assumptions that include 80% retention, a standard deviation (SD) for the PROMIS-PI of 8.0 T-score points in back pain cohorts, a serial correlation between repeated assessments  $\geq 0.35$ , and a MCID range for the PROMIS-PI of 2.0 - 3.5 T-score points for back pain. we tentatively estimate a sample size of 300 in each group (total 600 participants). This sample size provides  $> 90\%$  power with 2-sided significance in Aims 1 and 2 to detect differences in mean PROMIS-PI scores of 2.7 T-score points. This sample size will retain adequate power if retention rates are lower than anticipated, or if variability in PROMIS-PI scores is greater than anticipated. This sample size also retains 80% power to detect at least a difference of at least 3.3 T-score points for exploratory sub-group analyses described under Aim 3 for sub-groups with a prevalence of 50%. *See the SAP for additional details.*

***Secondary Sub-group Analyses (Aim 3):*** Sub-group analyses will be achieved by repeating the longitudinal analyses described for Aims 1 and 2 with the addition of a main effect term for the sub-group factor, and an interaction term between treatment and the sub-group factor, to the mixed effects models to estimate treatment effects within each sub-group and test interactions between treatment and the sub-group factor. Results will be interpreted as exploratory and displayed as forest plots with point estimates and 95% confidence intervals for each treatment comparisons provided for each subgroup.

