We will finalize the sub-grouping variables to be tested in the project Planning year. We plan to explore heterogeneity for the primary and select secondary outcomes based on gender, the presence of HICP, and current opioid use at the time of enrollment into the study. The presence of HICP is based on the GCPS-R which categorizes the impact of a person's chronic pain mild, bothersome or high impact. Current opioid use at baseline is categorized as short-term, episodic or long-term. For sub-group analysis we expect to examine long-term opioid users relative to those who are not long-term users. *See section D.9 for further details on baseline measurement procedures.*

***Implementation Outcomes (Aim 4):*** Consistent with a hybrid type I study design we will evaluate selected implementation outcomes as an aspect of our trial. (*see section D.9 for further details on implementation outcome measures*). In general, implementation outcomes will be examined descriptively with frequencies and percents for categorical outcomes and summary statistics including means, standard deviations, and relevant percentiles for numeric outcomes, with supplemental graphical displays using box plots, histograms and overlaid kernel density curves. We will also compute 95% confidence intervals for binary outcomes such as the percentage of patients asked about a pain teleconsult in clinics (*adoption*) and the percentage of patients accepting the consultation (*acceptability*), and for the cumulative percentages of treatment sessions attended (*feasibility*) and the cumulative percentage of core treatment components provided (*fidelity*) relative to the intended numbers specified by study protocols for the brief pain teleconsult and phone-based IT interventions. We may use linear mixed models or generalized estimating equations under general linear models as appropriate to provide complimentary assessments of differences in implementation outcomes between treatment groups.

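### Randomisation is stratified by opioid use, gender and HICP, but the co-primary model as described leaves these factors out, so its intervals are mildly conservative if the strata are prognostic

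*Protocol*

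**What the plan says.** **Randomisation (Protocol D.16).** "We will stratify randomization based on pre-specified sub-grouping variables opioid use, gender, presence of HICP". Site is mentioned as a possible further stratifier, to be considered in the Planning year.

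**Co-primary model (Protocol D.18.1, Aims 1 and 2).** A longitudinal mixed-effects analysis "of the primary effectiveness outcome scores (PROMIS-PI) at baseline, and across the 12-, 26-, and 52-week follow-ups", "assuming equal baseline mean PI scores across randomized groups to optimize statistical power". Linear contrasts between arms address Aim 1 at 12 weeks and Aim 2 at 52 weeks. No covariate is named.

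**Sub-group model (Protocol D.18.1, Aim 3).** This is obtained by "repeating the longitudinal analyses described for Aims 1 and 2 with the addition of a main effect term for the sub-group factor", together with a treatment-by-factor interaction. The factors are "based on gender, the presence of HICP, and current opioid use at the time of enrollment into the study".

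**Precision.** Testing is two-sided at 0.05, without adjustment across Aims 1 and 2. The plan claims more than 90% "power with 2-sided significance in Aims 1 and 2 to detect differences in mean PROMIS-PI scores of 2.7 T-score points".

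**The concern.** The three stratification variables are also the three sub-group variables. Aim 3 takes the Aims 1 and 2 analysis and adds the factor's main effect. A term that has to be added is not there to begin with, so the text goes beyond leaving covariates unmentioned. Because Aim 3 adds one factor at a time, no model described holds all three strata together.

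Stratified allocation balances the strata between arms and so removes between-stratum variation from the treatment contrast. A model that omits the strata still counts that variation as residual. Its standard error then describes a noisier design than the one used.

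The protocol gives some reason to expect prognostic strata. In D.9 it justifies pain interference as the primary outcome because "it reflects the degree to which pain interferes with daily activities, which is a hallmark of HICP". At stake are the width of the intervals and the nominal level of the tests for both co-primary contrasts.

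**Working it through.** **Inputs from Protocol D.18.1:** SD 8.0; serial correlation 0.35 (the stated lower bound); 300 per arm; 80% retention, so 240 per arm evaluable; two-sided 0.05; target difference 2.7; MCID range 2.0 to 3.5.

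**Assumed, not in the documents:** partial R² of the strata for follow-up PROMIS-PI given baseline PROMIS-PI, written r below.

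**1. The plan's own figures.** With a change-score variance, SD = 8 × √(2 × (1 − 0.35)) = 9.121 and SE = 9.121 × √(2/240) = 0.833. Power is 90.0% at 2.7 points, and 80.0% at 3.3 points in a half-size sub-group. Both stated figures are reproduced. The planned model, which uses the baseline score, corresponds at a single visit to SD = 8 × √(1 − 0.35²) = 7.494 and SE = 7.494 × √(2/240) = 0.684. Its power at 2.7 points is 97.7%. The stated power is therefore already cautious for that model.

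**2. Effect of omitting the strata.** With balanced strata:
- ratio of reported to true SE: k = 1/√(1 − r)
- true size of the unadjusted test: 2 × (1 − Φ(1.96 × k))
- 95% half-width: 1.96 × 0.684 = 1.341 unadjusted, and 1.341/k adjusted
- true power of the unadjusted test at difference d: Φ((d/0.684 − 1.96) × k)
- power of the adjusted test: Φ(k × d/0.684 − 1.96)

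| Assumed r | Adjusted half-width | Unadjusted too wide by | True size | Power at 2.7, unadj. / adj. | Power at 2.0, unadj. / adj. |
|---|---|---|---|---|---|
| 0.01 | 1.334 | 0.5% | 4.9% | 97.7% / 97.8% | 83.4% / 83.6% |
| 0.02 | 1.327 | 1.0% | 4.8% | 97.8% / 97.9% | 83.5% / 84.0% |
| 0.05 | 1.307 | 2.6% | 4.4% | 97.9% / 98.2% | 83.9% / 85.1% |
| 0.10 | 1.272 | 5.4% | 3.9% | 98.2% / 98.6% | 84.5% / 86.9% |

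**3. Simulation check.** 4,000 runs with no treatment effect, N = 480, permuted blocks of 4 within 8 strata and one follow-up visit. The baseline score is in both models. Prevalences and effects (in points, for HICP / opioid use / gender) are assumed.

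| Effects | Unadjusted: model SE / empirical SD / rejection | Adjusted: model SE / empirical SD / rejection |
|---|---|---|
| 4 / 3 / 1 | 0.696 / 0.674 / 4.2% | 0.664 / 0.669 / 5.3% |
| 2 / 2 / 1 | 0.674 / 0.663 / 4.6% | 0.663 / 0.662 / 5.0% |
| 1 / 1 / 0.5 | 0.666 / 0.676 / 5.5% | 0.664 / 0.677 / 5.5% |

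The Monte Carlo error of a rejection rate is about √(0.05 × 0.95/4000) = 0.3 percentage points. The empirical SD is almost the same in both models, so the point estimate loses little. What is overstated is the reported SE, and only when the strata are clearly prognostic.

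**The case against.** **The SAP may supply the terms.** Protocol D.18 calls itself an overview, defers detail to the SAP, and makes finalising the SAP a planning milestone. A bare absence of covariates would be no finding. This objection limits confidence but does not remove the point: an SAP that adjusted for the strata would depart from how D.18.1 relates the Aim 3 model to the co-primary one. The two should be made to agree.

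**The Aim 3 sentence may be a generic template.** The sub-group list is still to be finalised. Aim 3 expects to contrast long-term opioid users with all others, whereas D.16 gives no levels for the opioid stratum. A dichotomised sub-group term could be added to a model already holding a differently coded stratum. This is fair: the overlap is shown for the variables, not for their coding. The correction should therefore refer to the factors as randomised.

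**The size is assumed, and baseline PROMIS-PI may absorb much of HICP.** This stands. Nothing in the documents fixes r, and the weakest simulated scenario shows practically no difference.

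**Stronger readings.** A reader might infer lost sample size from 480 × r/(1 − r), which gives 10, 25 or 53 of the 480 completers at r = 0.02, 0.05 or 0.10. That formula equates reported interval widths, not power. Equating power at 2.7 points under the formulas above gives about 5, 12 or 25 participants. A reader might also infer an invalid test or an underpowered trial. Neither follows: the error is conservative, and power stays above 90% at 2.7 points.

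**Conclusion.** The point holds in a limited form. As described, the co-primary model does not include the factors used to stratify randomisation. If those factors predict follow-up PROMIS-PI beyond its baseline value, the model-based standard errors of both contrasts are conservative. Over an assumed partial R² of 1% to 10%, that means intervals about 0.5% to 5% too wide and a true size of about 4.9% to 3.9%. The largest gain in power in that range, at the lower MCID bound of 2.0 points, is from 84.5% to 86.9%.

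The treatment estimate is not biased, type I error is not inflated, and the sample size is not called into question. The figures rest on a single-visit approximation to the longitudinal model, the protocol's SD, correlation and retention, and the assumed R². This is a free improvement rather than a flaw that threatens the conclusions.

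**What to change.** 1. State in D.18.1 and the SAP that the co-primary mixed model includes the randomisation stratification factors, coded as randomised: opioid use, gender, HICP, and site if it becomes a stratifier. Enter them as fixed covariates with factor-by-visit terms. Baseline PROMIS-PI is part of the outcome vector in the constrained-baseline model, so a single main effect would force the same stratum shift at baseline and at every follow-up.
2. Include the same factors in the analogous secondary-outcome models.
3. Reword Aim 3 as adding the treatment-by-factor interaction, plus the factor's main effect only where it is not already in the model, for instance because the sub-group coding differs from the stratum coding.

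The factors would then also enter the imputation models, since D.18.2 carries over all variables of the outcome model. The cost is wording only: the values are needed before randomisation anyway, so no new data are required. It should be settled before any unblinded analysis, so that the choice between adjusted and unadjusted results is not made after seeing them.

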## **RESOURCE SHARING PLAN**

We are committed to open and timely dissemination of research outcomes of our study and study data with appropriate privacy and confidentiality protections to facilitate further research, reuse of data, and replication. Sharing of data generated by this project will be an important part of the proposed activities of this research and will be carried out in several ways. All research resources developed in this project (manuals, policies, protocols, etc.) will be made readily available to the scientific community for non-profit research purposes. All investigators in this proposal will abide by the principles for sharing research resources, as described by NIH in “Principles and Guidelines for Recipients of NIH Research Grants and Contracts on Obtaining and Disseminating Biomedical Research Programs” All data and resources will be shared consistent with the guidelines and policies of the NIH, the NIH HEAL Initiative and as developed by the Steering Committee of the PRISM Program.

## **DATA SHARING PLAN**

Sharing data generated by this project will be carried out in several ways. Data generated will be presented at national or international conferences and published in the scientific literature in a timely fashion. All final peer-reviewed manuscripts that arise from this project will be submitted to the digital archive PubMed Central. We will make our data available to the community of scientists interested in implementing strategies to enhance the uptake of evidence-based practices and to improve outcomes for patients with low back pain. We will comply with the Data Sharing Policy developed by the Health Care Systems Collaboratory Steering Committee ([https://www.nihcollaboratory.org/Products/Collaboratory.DataSharingPolicy\\_June232014.pdf](https://www.nihcollaboratory.org/Products/Collaboratory.DataSharingPolicy_June232014.pdf)) and as specified in the NIH HEAL Initiative Public Access and Data Sharing requirements (<https://heal.nih.gov/about/public-access-data>).

Any data shared upon request will be de-identified and released only after documentation (e.g., data sharing agreements) as appropriate is completed by the relevant entities. Users must agree to the conditions of use governing access to the public release data, including restrictions against attempting to identify study participants, destruction of the data after analyses are completed, reporting responsibilities, restrictions on redistribution of the data to 3rd parties, proper acknowledgement of the data resource, information provided to users will not be used for commercial purposes, and will not be redistributed to third parties.
